Growing evidence indicates that vitamin D's effect on reducing falls is mediated by improvements in neuromuscular function.⁶⁻⁸ We and others have shown associations between 25(OH)D concentrations and muscle strength and physical performance measures associated with fall risk (e.g., gait, balance) in observational studies.^{6,9-13} Yet trials of vitamin D supplementation on changes in muscle strength and physical performance are equivocal,¹⁴ likely due to inadequate trial duration, small sample sizes, insufficient vitamin D dose, and sample heterogeneity. Moreover, vitamin D's effects on the mechanisms underlying neuromuscular function are not well understood. Determining whether increasing 25(OH)D concentrations to ≥ 30 ng/mL will improve neuromuscular deficits that are risk factors for falls and elucidating the underlying physiological mechanisms linking vitamin D and neuromuscular function could change clinical practice by providing evidence to guide vitamin D supplementation recommendations for neuromuscular-related outcomes in older adults.

Objectives

To conduct a 12-month, double-blind randomized placebo controlled trial in 136 older (65-89 yrs) men and women with initial 25(OH)D concentrations of 18- <30 ng/mL to determine the effect of increasing 25(OH)D concentrations to ≥ 30 ng/mL through vitamin D₃ supplementation on 1) change in neuromuscular functions that are established risk-factors for falls in older adults; and 2) changes in the underlying physiological mechanisms over 4 months in a subset of 36 randomly selected participants. Participants will be randomized to 2000 IU/d of vitamin D₃ (a dose expected to increase 25(OH)D concentrations by ~ 14 ng/mL) or placebo.

Hypothesis 1: Compared to participants randomized to placebo, participants randomized to vitamin D₃ will have increased lower extremity muscle power and strength, increased physical performance, decreased postural sway, and reduced rate of falls over 12 months.

Hypothesis 2: Compared to participants randomized to placebo, participants randomized to vitamin D₃ will have increased type II muscle fibers, muscle fiber force, and myofiber regeneration, and decreased muscle fiber denervation over 4 months.

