The second 4-month follow-up visit (4FV2) will occur 3-5 days after the 4FV1 visit in the morning for participants in the muscle biopsy substudy who had a viable muscle biopsy sample at BV2 only. After an 8-hour overnight fast, participants will undergo a muscle biopsy of the *vastus lateralis* followed by a snack. Participants will receive a phone call 2-4 days following the procedure to check that they are not experiencing any adverse effects that may be related to the procedure. The study physician ([name]) will be notified of any adverse effects related to the muscle biopsy procedure and any necessary action taken.

The 12-month follow-up visit (12FV) will occur during week 52 of the intervention. After an 8-hour overnight fast, participants will have their vitals taken and blood drawn for analyses of serum 25(OH)D and 1,25(OH)D, plasma PTH, metabolic panel, and storage followed by a snack. Lower extremity muscle power and strength, physical performance, grip strength, postural sway, stair climb, and gait velocity will be measured. The CHAMPS Physical Activity Questionnaire, MAT-sf, arthritis and joint pain questionnaire, DSST, CES-D, the MoCA, and sun exposure questionnaire will be administered. Medical history and current medications and dietary supplements will be reviewed. Monthly fall calendars will be collected and reviewed. Participants will return the study supplement bottles with any remaining pills. Participants will then be told of their randomization assignment.

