We will examine the distributions of all continuous outcomes of interest, and will transform them to approximate normality if the outcomes show a strong departure from normality as evidenced by examining Q-Q plots and performing the Shapiro-Wilk test. Outliers will be examined on the chosen scale (original or transformed) and may be set to missing if they are 3 or more interquartile ranges above the 75th percentile or below the 25th percentile. Plausible biologic values may be retained even if they are outliers. Implausible biologic values may be set to missing based on a review of health-related events (e.g., AEs related to pain, fractures, surgery) in the interval surrounding the collection of the measurements.

The primary outcome for this trial will be the 12-month measure of muscle power. For the muscle biopsy substudy, the primary outcome will be the change in type II muscle fibers over 4-months. Our primary statistical analyses will proceed on the “intent-to-treat” principle in which data from all randomized participants are used to test the primary hypotheses that compared to placebo, vitamin D₃ supplementation will result in increases in lower extremity muscle power and strength, and improvements in physical performance (expanded SPPB, TUG, and 20-m walk speed) and balance. Even if participants wish to discontinue the supplements, we will still attempt to follow them for outcomes in order to carry out intent-to-treat analysis at 12 months. Characteristics of the participants missing the 12-month follow-up outcomes will be compared to participants without missing data using chi-square tests and t-tests to determine if there are any differences with regard to intervention group, demographic characteristics, and baseline neuromuscular function outcomes. If a particular group exhibits markedly higher drop-out rates, we will attempt to identify baseline covariates that predict attrition. If such covariates can be identified, the analyses of outcome measures may need to be stratified according to these comparisons to decrease bias. We will use a mixed model with an unstructured covariance matrix to model after-treatment neuromuscular function outcomes between the two groups by time, with adjustment for

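### Outcome values judged implausible (undefined) may be set to missing after adverse-event review, which departs from the stated ITT analysis and can bias the primary contrast in either direction

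*Combined protocol and SAP*

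**What the plan says.** The first paragraph of Statistical Analyses has three linked provisions. Outliers, on the original or transformed scale, "may be set to missing if they are 3 or more interquartile ranges above the 75th percentile or below the 25th percentile". Next, "Plausible biologic values may be retained even if they are outliers". Last, "Implausible biologic values may be set to missing based on a review of health-related events (e.g., AEs related to pain, fractures, surgery", where the events are those in the interval around the measurement. All three are permissive. The last has no numeric limit, definition, decision-maker, timing, statement of blinding, or companion analysis with the values kept.

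The next paragraph of the same section says: "The primary outcome for this trial will be the 12-month measure of muscle power". It commits to an intent-to-treat analysis in which "data from all randomized participants are used to test the primary hypotheses". Under Objectives, Hypothesis 1 expects, among other benefits, "decreased postural sway, and reduced rate of falls over 12 months".

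**The concern.** The rule uses a post-randomisation event to decide whether a measured outcome counts. The event is poor evidence of measurement error: if someone has had a fracture, low leg power is what one would expect. The usual grounds for removal, such as equipment or recording error, are not mentioned.

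The trial expects treatment to reduce falls, and falls cause some fractures and painful injuries. If such events are commoner in one arm, that arm loses more low values. The contrast then drifts from the effect in everyone randomised towards an effect with the event pathway removed.

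The missing-data plan does not repair this. The mixed model also uses baseline and 4-month data, and the plan considers imputing the 12-month outcome from the 4-month one. A real post-event value could therefore be replaced by a prediction from before the event. The planned comparison of participants with and without 12-month data covers arm, demographics and baseline function, but not adverse events.

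**Working it through.** **Inputs from Statistical Power:** target difference 0.174 W/kg (10% of 1.74); preliminary SD 0.382; baseline mean 1.7 and SD 0.444; baseline-to-12-month correlation 0.708; 125 analysable participants, 1:1; two-sided 0.05. **Assumptions:** event rates near the visit, and the loss of power per event. The documents give neither.

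**1. The plan's own figure.** ANCOVA residual SD = 0.444 × √(1 − 0.708²) = 0.314. SE of the difference = 0.314 × √(2/62.5) = 0.056. Power = Φ(0.174/0.056 − 1.96) = 87.3%, or 85.8% with a difference of 0.17. The stated power above 80% is reproduced.

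**2. Shift if every event-related value is deleted.** Shift ≈ (rate on placebo − rate on vitamin D) × loss. Simulations used ANCOVA on baseline, with a direct treatment effect of 0.174.

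| Assumed rates, placebo / vitamin D | Assumed loss, W/kg | Shift, W/kg | Share of 0.174 | Simulated estimate, kept → deleted |
|---|---|---|---|---|
| 10% / 5% | 0.6 | 0.05 × 0.6 = 0.030 | 17% | 0.204 → 0.174 |
| 5% / 2% | 0.5 | 0.03 × 0.5 = 0.015 | 9% | 0.188 → 0.173 |
| 5% / 10% | 0.5 | −0.05 × 0.5 = −0.025 | 14% | 0.148 → 0.173 |

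In the first two rows deletion discards part of a true benefit. In the third it hides a cost of treatment and flatters vitamin D. Against the SE of 0.056, a shift of 0.030 is about half a standard error (0.030/0.056 = 0.54).

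**3. Equal event rates, no treatment effect, deletion blind to arm.** At 10% in both arms and a 0.5 W/kg loss, the mean estimate is −0.0015 W/kg with values kept and with values deleted, and the rejection rate is 4.6% after deletion. There is no bias and no excess type I error.

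**4. Equal event rates, but a true effect.** Rates are 10% in both arms, the loss is 0.5 W/kg, and a value is deleted only when it lies more than 0.4 W/kg below baseline. On average 3.8 placebo and 2.5 vitamin D values go, and the estimate falls from 0.175 to 0.164. Treated participants cross the threshold less often, so equal event rates alone do not protect the contrast.

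**5. Reach of the 3-IQR rule.** Under normality the lower fence is the mean minus 4.72 SD: 1.74 − 4.72 × 0.382 = −0.06 W/kg, or 1.7 − 4.72 × 0.444 = −0.40 W/kg. On the original scale that rule can never remove a low leg-power value. On a log scale the fence is about 0.49 to 0.61 W/kg.

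**The case against.** The strongest reply is that the rule is narrow. It covers only values judged implausible, and the preceding sentence lets plausible outliers stay. A loss of 0.6 W/kg from a mean of 1.7 leaves 1.1 W/kg, only 0.6/0.444 = 1.35 SD down and quite ordinary. If the sentence is only the last step of the 3-IQR screen, no low primary value could go on the original scale. On a log scale about 8% of values lowered by 0.6 W/kg would fall below the fence: with 10% and 5% injured in arms of 61, 61 × 0.10 × 0.08 ≈ 0.5 and 61 × 0.05 × 0.08 ≈ 0.2 values. This stands as a limit on size. It does not remove the problem, because the text does not say which reading applies and leaves implausible undefined.

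Three stronger readings are tempting, but the documents do not support them.

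- A reader might infer that any value recorded after pain, a fracture or surgery can be dropped. The text requires a judgement of implausibility as well.
- A reader might infer that the review is unblinded, because at the 12-month visit "Participants will then be told of their randomization assignment". That sentence concerns participants. It does not say that data reviewers learn the assignment, and no cleaning date is given. Outcome assessors are blinded. The coordinator who asks about adverse events also checks 4-month 25(OH)D in participants assigned to vitamin D, but nothing says the coordinator decides on removals. What can be said is that blinding of this review is not stated.
- A reader might infer an inflated type I error. Dropping the three lowest values in one arm of 61 under the null does raise it to about 7%, but one-arm deletion is not what the plan authorises.

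The causal argument is also partial: Hypothesis 1 names falls, an exploratory outcome, and does not name pain or surgery. Nor should every recorded number be kept. Outcome measures requires maximal effort for leg power, and Potential Risks has tests stopped for pain, so an aborted trial is not a valid measurement.

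**Conclusion.** The concern holds in a limited form. The plan lets values judged implausible, without a definition, be set to missing after adverse-event review, and does not state that this review is blinded. This conflicts with the commitment to analyse everyone randomised and can bias the 12-month leg-power contrast either way.

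The size cannot be derived from the documents. The 17% and 9% figures rest on assumed event rates and losses and on deletion of every event-related value; they are upper bounds for those assumptions, not estimates. The bias is nil when event rates are equal, treatment has no effect and the review is blind. The case for change rests on the rule being avoidable and cheap to correct, not on a demonstrated large bias.

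**What to change.** Replace the adverse-event sentence in Statistical Analyses with the following.

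- **Primary ITT analysis:** keep every validly obtained measurement, including values lowered by a health event.
- **Set to missing only documented measurement failures:** equipment or recording error, a physically impossible value, or an aborted or invalid trial.
- **Process:** written criteria, a named role that decides, and decisions taken before database lock, blind to arm and to 25(OH)D. Log each removal and report removals by arm and reason.
- **Sensitivity analysis:** use adverse-event-based and 3-IQR exclusions only here, labelled as such, and state the scale on which the 3-IQR rule is applied.

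The cost is a few sentences and one extra model run. Sample size and alpha do not change. The downside is that a few extreme true values stay in and may widen the confidence interval slightly.

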Lower extremity muscle strength and power, physical performance, and postural sway will be assessed at baseline, 4 months and 12 months and falls assessed monthly. Muscle biopsies of the *vastus lateralis* will be taken at baseline and 4 months to assess muscle fiber type, contractility, and denervation, and number and differentiation stage of satellite cells. The primary outcomes are change in lower extremity muscle power (Hypothesis 1) and change in percentage of type II (fast-twitch) muscle fibers (Hypothesis 2). Secondary outcomes include change in lower extremity muscle strength, physical performance, and postural sway (Hypothesis 1) and muscle fiber contractility, muscle fiber denervation, and number and differentiation of satellite cells (Hypothesis 2). Falls will also be assessed as an exploratory outcome (Hypothesis 1).

Methods and Measures

Experimental Overview/Study Design

This study is a 12-month, double-blind randomized placebo controlled trial in 136 older (65-89 yrs) men and women with initial 25(OH)D concentrations of 18-<30 ng/mL to determine the effect of increasing 25(OH)D concentrations to ≥ 30 ng/mL through vitamin D₃ supplementation on 1) change in neuromuscular functions that are established risk-factors for falls in older adults and 2) changes in the underlying physiological mechanisms over 4 months in a subset of 36 randomly selected participants. Participants will be randomized to vitamin D₃ (2000 IU/d) or matching placebo in a 1:1 ratio stratified by gender and race.

Recruitment of study participants

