We plan to recruit and randomize a total of 136 older men and women with baseline 25(OH)D concentrations of 18-<30 ng/mL to 2000 IU/d vitamin D₃ or matching placebo for 12 months in a 1:1 ratio stratified by gender and race. In addition, a subset of participants that are eligible to receive the muscle biopsy, i.e. those not taking anti-coagulants, will be randomly selected in a 1:1 ratio stratified by gender and race to be included in the 4 month muscle biopsy mechanistic substudy. We will stop recruitment into the muscle biopsy substudy when we can ensure that at least 32 participants will complete the pre- and post-muscle biopsy. Our power analyses show that 125 persons total (assuming 90% retention) will yield >80% power to detect between group differences of a 10% relative increase in lower extremity muscle power and 16 persons/group (assuming 32 completers) will yield >80% power to detect a 25% difference in the relative increase in type II muscle fibers between groups in the muscle biopsy substudy. We plan to recruit, screen, and enroll these individuals continuously at the rate of approximately 5-6/mo during years 1-4 of the study. We will target men and women aged 65 to 89 years who live in the surrounding area via media advertisements (newspaper), targeted mass mailings, the VITAL newsletter, and community outreach events. We will also target age-eligible patients being seen at the Downtown Health Plaza (DHP) via posters, flyers, targeted mass mailing, and approaching age-eligible patients following their scheduled DHP care provider visit to see if they would be interested in learning more about the study.

Participant screening and randomization

Telephone screening. All prospective participants will initially be screened via telephone to determine general eligibility. They will be asked about their age, medical history, and current medications and dietary supplements. All participants must meet the inclusion/exclusion criteria in **Table 1**. These selection criteria will eliminate participants with conditions that may affect their ability to safely perform the neuromuscular function tests, consume vitamin D supplements, or undergo a muscle biopsy. The telephone screen will be administered in person to interested DHP patients following their scheduled DHP care provider visit if time allows by the DHP recruitment coordinator; otherwise, it will be administered over the phone.

Inclusion Criteria	Exclusion Criteria

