Screening, consent and randomization. Individuals who pass the telephone screening will be scheduled for a screening visit (SV) in the Geriatric Research Clinic (GRC) in the Sticht Center on Aging. Before any data collection, all participants will provide written informed consent and complete a HIPAA authorization form in accordance with the Wake Forest School of Medicine Institutional Review Board policies. DHP patients who pass the in-person telephone screen will be given the option of completing a prescreen visit (PSV; informed consent, MoCA, SPPB, and weight and height for BMI; see below) with the DHP recruitment coordinator at the DHP after their scheduled DHP care provider visit if time allows. If they are eligible following the prescreen visit, they will be scheduled for the full screening visit at the GRC.

Individuals who meet all eligibility criteria and provide informed consent will be invited back for the first baseline visit 1 (BV1). At the end of BV1, participants will be randomized to participate in the muscle biopsy substudy (those who are not on anti-coagulants) using a web-based randomization scheme (developed by [name]) with blocking by gender and race with a goal of achieving $n=32$ pre- and post-muscle biopsy samples. At the end of baseline visit 2 (BV2), participants will be randomized to one of the two study interventions (vitamin D₃ or placebo) using a web-based randomization scheme (developed by [name]) with blocking by gender, race, and muscle biopsy subgroup. Block size and the randomization sequences will be unknown to the research staff. Muscle biopsy and intervention assignment will be generated using a program that the study coordinator will access from her PC through the study website.

Schedule and organization of assessment visits

All assessments will be conducted during 5-6 visits according to the timeline in **Table 2**: 1 screening visit; 2 baseline visits; 1 or 2 (participants undergoing a muscle biopsy only) 4-month mid-intervention follow-up visits; and 1 12-month post-intervention follow-up visit. Assessments will take place in the Geriatric Clinical Research Unit, the Geriatric Research Clinic, or the Downtown Health Plaza (prescreen visit only).

Activity/assessment	Visit code	SV	BV1	BV2	On trial	4FV1	4FV2	12FV
		-3	-1	0		16	17	52

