the baseline neuromuscular function measure, age, gender, and race, using data from baseline, 4, and 12 months, and estimating the baseline to 12 month change using linear contrasts. In secondary analyses, we will fit linear contrasts to compare whether the change between the two groups at 4 months differs from the change at 12 months. These analyses will be adjusted for age, gender, race, and season, as we anticipate there will be an effect of season on the change from baseline and 12 months. If the analyses of the characteristics of those missing the 12-month outcome data indicate that the missing data are informative, we will also consider using the 4-month outcome data to impute the 12-month outcome, using the trajectory models to predict the 12-month outcome.

We will examine factors that may influence the measured responses to the intervention. We anticipate that not all individuals will respond to the vitamin D₃ dose in a similar manner due to genetic differences⁵⁰⁻⁵² as well as differences in BMI,^{53,54} health status, and adherence.³ First, individuals in the vitamin D intervention group who have low adherence (<80%) will be excluded from the analysis. We will also investigate treatment effects by attained 25(OH)D concentrations including only those in the intervention group whose 12-month 25(OH)D concentrations are ≥30 ng/mL. We will also fit models that include BMI, health status, and other variables to determine if they account for any of the variation in response to the intervention on changes in the outcomes. For our exploratory outcome of falls, we will use a generalized estimating equation (GEE) approach to model repeated measures, assuming a Poisson distribution, to compare the rate of falls in each group with adjustment for age, gender, and race.⁵⁵ Differences in, or reasons for, attrition rates between study groups may complicate the analysis of the primary outcomes. Therefore, the attrition rates will also be compared and, if a particular group exhibits markedly higher drop-out rates, we will attempt to identify baseline covariates that predict attrition. If such covariates can be identified, the analyses of outcome measures may need to be stratified according to these comparisons to decrease bias.

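### Treatment assignment is blocked by gender, race and muscle biopsy subgroup, but the full-trial models adjust only for gender and race: a small omission that is cheap to close

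*Combined protocol and SAP*

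**What the plan says.** The operational account of treatment allocation is under Screening, consent and randomization. At the end of BV2, participants are assigned to vitamin D₃ or placebo "with blocking by gender, race, and muscle biopsy subgroup". Biopsy status is already known by then, because it is drawn at the end of BV1.

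Three other sections describe the strata without the biopsy subgroup. Experimental Overview/Study Design says: "Participants will be randomized to vitamin D₃ (2000 IU/d) or matching placebo in a 1:1 ratio stratified by gender and race". Recruitment of study participants and Statistical Power likewise name gender and race only.

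The biopsy subgroup is a random draw with one clinical restriction. Among the eligible, "those not taking anti-coagulants, will be randomly selected in a 1:1 ratio stratified by gender and race" for the substudy, and substudy recruitment stops once 32 completers can be assured.

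Statistical Analyses lists these covariates for the full trial:

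- Main mixed model for neuromuscular outcomes: "the baseline neuromuscular function measure, age, gender, and race".
- Secondary contrasts of 4 against 12 months: "These analyses will be adjusted for age, gender, race, and season".
- Falls GEE: "to compare the rate of falls in each group with adjustment for age, gender, and race".

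No reason is given for leaving out the biopsy subgroup. The only open-ended wording, "We will also fit models that include BMI, health status, and other variables", belongs to the exploratory models of response to the intervention and does not name it.

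**The concern.** Blocking on a factor removes its chance imbalance between arms, so the true sampling variance of the treatment difference falls. A model without the factor leaves its contribution in the residual. The reported standard error is then larger than the true one whenever the factor predicts outcome. The plan follows the usual rule for two of its three blocking factors and not for the third.

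There are two reasons why the subgroup might carry some prognostic information. Every anticoagulant user falls in the non-biopsy stratum. Once the substudy closes, everyone enrolled later is also non-biopsy, so the factor partly follows calendar time. Willingness to be biopsied is not a third reason, because unwillingness is an exclusion criterion for the whole trial.

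Separately, the sections disagree on the strata, so a reader cannot be sure which scheme was programmed.

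**Working it through.** **1. The plan's own figure.** Inputs from Statistical Power: difference 0.174 W/kg, SD 0.444, baseline to 12-month correlation 0.708, 125 participants (62.5 per arm), two-sided 0.05.

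- Residual SD = 0.444 × √(1 − 0.708²) = 0.3136.
- SE = 0.3136 × √(2/62.5) = 0.0561.
- Power = Φ(0.174/0.0561 − 1.96) = 87.3%.

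The stated power of more than 80% is reproduced.

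**2. From a subgroup gap to the standard error.** Let p be the biopsy fraction and d the adjusted 12-month gap between biopsy and non-biopsy participants, in residual SDs. The share of residual variance is R² = p(1 − p)d², and the SE is too wide by 1/√(1 − R²) − 1. With p = 36/136 = 0.265:

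- d = 0.2: R² = 0.0078, SE 0.4% too wide.
- d = 0.5: R² = 0.0487, SE 2.5% too wide.

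Both values of d are assumptions. To reach 1%, R² must be 0.0197, which needs d = √(0.0197/0.1946) = 0.32.

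**3. How large d could be through anticoagulant use.** Let q be the fraction of all participants on anticoagulants and D their adjusted deficit in residual SDs. The documents give neither. Non-biopsy participants are 100/136 = 0.735 of the trial, so d = qD/0.735.

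| q | D | d | SE too wide by |
|---|---|---|---|
| 5% | 0.3 | 0.02 | 0.004% |
| 10% | 0.5 | 0.07 | 0.05% |
| 20% | 1.0 | 0.27 | 0.7% |

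For d = 0.5, qD must be 0.37, a deficit of 1.8 SD at q = 20% or 3.7 SD at q = 10%, after adjustment for baseline power. Even d = 0.2 needs a deficit of about 1.5 SD at q = 10%.

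**4. Effect on the test.** In closed form, with total residual SD held at 0.3136, type I error without the term is 2[1 − Φ(1.96/√(1 − R²))]. Power without the term is Φ((0.174 − 1.96 × 0.0561)/(0.0561√(1 − R²))). With the term, the SE itself shrinks by √(1 − R²).

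| Assumed R² | Type I error without term | Power without | Power with |
|---|---|---|---|
| 0 | 0.050 | 87.3% | 87.3% |
| 0.02 | 0.048 | 87.6% | 88.0% |
| 0.05 | 0.044 | 87.9% | 88.9% |

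**5. Simulation check.** The simulation had 4,000 runs, 126 participants of whom 33 were biopsied, and blocks of 4 within gender × race × biopsy. Block size and the gender and race mix are assumptions. The gap is added on top of the residual SD.

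| Assumed gap, W/kg | Type I error without / with | Power without / with |
|---|---|---|
| 0 | 0.048 / 0.048 | 86.6% / 86.5% |
| 0.1 | 0.048 / 0.050 | 86.7% / 87.1% |
| 0.2 | 0.040 / 0.045 | 85.1% / 87.0% |

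A gap of 0.2 W/kg is 0.2/0.3136 = 0.64 residual SD, beyond the upper value in step 2. Even there the loss is about 2 points of power.

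**6. Not calculated.** The calendar-time route has no figure in the documents. The variance formula above is for a linear model and does not carry over to the Poisson GEE for falls.

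**The case against.** The strongest reply is that the factor is close to noise by design. Selection is random and itself stratified by gender and race, which are already in the model. The model also adjusts for age and the baseline outcome, which should absorb much of any difference due to anticoagulant use. Nothing in the documents suggests that enrolment date predicts 12-month power once baseline power is known. The blocking also looks operational: it helps to secure equal arms in a substudy that needs 16 per group. On this view the omission is a matter of taste, and the gender-and-race wording elsewhere is only a summary.

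Most of this stands, and it limits the size of the point. It does not remove the mismatch. A purely operational blocking factor is still part of the design, no reason for omitting it is given, and the plan adjusts for the other two.

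A reader might infer more than the documents support:

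- **Bias or false positives.** The factor is fixed before treatment assignment and balanced by the blocking, so leaving it out does not bias the estimate, and the direction is conservative.
- **An underpowered trial.** The stated power holds with or without the term.
- **An established loss of 0.4% to 2.5%.** That range rests wholly on the assumed gap of 0.2 to 0.5 SD, and step 3 shows that anticoagulant use would seldom reach even its lower end.
- **An error in the substudy ANCOVA.** It includes biopsy participants only, so the factor is constant there.

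**Conclusion.** The point holds as a minor, nearly free improvement. On the detailed randomisation description, treatment is blocked on three factors and the full-trial models carry two. The likely cost is well under 1% of the standard error, and 2.5% is an unlikely upper bound that needs a gap of 0.5 residual SD. Both statements rest on assumptions about how strongly the subgroup predicts outcome. For falls, an exploratory outcome, the case is consistency only.

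The disagreement over strata is a separate textual defect that does not depend on any effect size. If the gender-and-race scheme were the one actually programmed, the mismatch with the models would disappear and the detailed description would be the text to correct.

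**What to change.** - In Statistical Analyses, add muscle biopsy subgroup (yes/no) as a pre-specified fixed effect in the mixed model for the primary and secondary full-trial outcomes, including the 4- versus 12-month contrasts. Add it to the falls GEE for consistency.
- Confirm which factors the web-based scheme uses. If biopsy subgroup is one, add it to the stratification statements in Experimental Overview/Study Design, Recruitment of study participants and Statistical Power.
- If the term is deliberately left out, state the reason before the data are unblinded.
- Leave the biopsy substudy ANCOVA as it is.

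The cost is one degree of freedom per model, as a main effect, and a line or two of text. No new data are needed and the sample size does not change. Settling it now also removes a later choice between models with and without the term.
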